2.3. Hypotheses

All primary hypotheses must be met in order to satisfy the study objective.

Primary Hypotheses

- 1. After approximately 2 weeks of wear in the optimized lenses, the mean overall quality of vision score with the Test lens will be statistically better than 40 points on CLUE scale for myopic subjects.
- 2. After approximately 2 weeks of wear in the optimized lenses, the mean overall quality of vision score with the Test lens will be statistically better than 32 points on CLUE scale for hyperopic subjects.

- 3. After approximately 2 weeks of wear in the optimized lenses, the binocular, high-luminance, high-contrast distance (4 M) logMAR visual acuity of the test lens will be statistically better than 0.00 logMAR. This will be determined using ETDRS LogMAR acuity testing charts.
- 4. After approximately 2 weeks of wear in the optimized lenses, the binocular, high-luminance, high-contrast intermediate (64 cm) logMAR visual acuity of the test lens will be statistically better than +0.17 logMAR. This will be determined using Guillon/Poling LogMAR acuity testing charts.
- 5. After approximately 2 weeks of wear in the optimized lenses, the binocular, high-luminance, high-contrast near (40 cm) logMAR visual acuity of the test lens will be statistically better than +0.17 logMAR. This will be determined using Guillon/Poling LogMAR acuity testing charts.

Secondary Hypotheses

Secondary hypotheses will be tested for the hyperopes and the myopes separately.

- 1. After approximately 2 weeks of wear in the optimized lenses, the mean overall quality of vision CLUE score for Test lens will be non-inferior to the baseline score measured for habitual correction. A non-inferiority margin of -5 will be used.
- 2. After approximately 2 weeks of wear in the optimized lenses, the mean comfort CLUE score with the Test lens will be non-inferior to the baseline score measured for habitual correction. A non-inferiority margin of -5 will be used.
- 3. After approximately 2 weeks of wear in the optimized lenses, the mean lens handling CLUE score with the Test lens will be non-inferior to the baseline score measured for habitual correction. A non-inferiority margin of -5 will be used.

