5. TEST ARTICLE ALLOCATION AND MASKING

5.1. Test Article Allocation

This is a single-arm study. All subjects will be dispensed the study lens in a bilateral fashion.

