14.5. Primary Analysis

CLUE Vision Scores

Vision scores after approximately 2-weeks in the optimized lenses will be analyzed using a linear mixed model. Baseline vision scores, event (visit 1: baseline, visit 2: 1-wk non-optimized, visit 3: 1-wk optimized and visit 4: 2-wk optimized), strata (hyperope and myope) and the interaction between event and strata will be included in the model as fixed effects. Other covariates such as age, gender and add power may be included when appropriate. Site will be included as a random effect (G-side). Residual errors between measurements within the same subject across event will be model using one of the following:

- Unstructured (UN)
- Compound Symmetric (CS)

• Heterogenous Compound Symmetric (CSH)

The structure that returns the lowest corrected Akaike's Information Criterion (Keselman et al. 1998)¹³ will be selected as the structure that best fits the data. The Kenward and Roger method will be used for the calculation of the denominator of degrees of freedom.¹⁴

Primary hypothesis 1:

The null and alternative hypothesis for CLUE vision to test for superiority of the Test lens relative to the pre-defined threshold of 40 for myopes is as follows:

$$H_o$$
: $\mu_{Test} \le 40$
 H_A : $\mu_{Test} > 40$

Superiority will be declared if the lower limit of the 95% confidence interval of the adjusted mean for the Test lens is greater than 40. i.e. $P(\mu_{Test} > 40) \ge 0.975$.

Primary hypothesis 2:

The null and alternative hypothesis for CLUE vision to test for superiority of the Test lens relative to the pre-defined threshold of 32 hyperopes is as follows:

$$H_o$$
: $\mu_{Test} \le 32$
 H_A : $\mu_{Test} > 32$

Superiority will be declared if the lower limit of the 95% confidence interval of the adjusted mean for the Test lens is greater than 32. i.e. $P(\mu_{Test} > 32) \ge 0.975$.

LogMAR Visual Acuity

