Binocular, high luminance, high contrast visual acuity on logMAR scale after approximately 2-weeks in the optimized lenses will be analyzed using a linear mixed model. Position(distance/intermediate/near) will be included as the only fixed effect. Site will be included as random effect (G-side). Other baseline characteristics known of importance such as age, gender and add power may be included as covariates when appropriate. The covariance between residual errors from the same subject across different positions will be selected based on the finite-sample corrected Akaike's Information Criterion (Keselman et al. 1998). Covariance structures considered may include: Homogenous compound symmetry (CS) and Unstructured covariance structure (UN). The structure that returns the lowest Akaike Information Criteria Corrected (AICC) will be selected as the structure that best fit the data. The Kenward and Roger method will be used for the calculation of the denominator of degrees of freedom. Acres of the calculation of the denominator of degrees of freedom.

Primary hypothesis 3:

The null and alternative hypothesis for binocular distance HLHC visual performance to test for superiority of the Test lens relative to the pre-defined threshold of 0 logMAR is as follows:

$$H_o$$
: $\mu_{Test} \ge 0 \log MAR$
 H_A : $\mu_{Test} < 0 \log MAR$

Superiority will be declared if the upper limit of the 95% confidence interval of the adjusted mean for the Test lens is below 0 logMAR. i.e. $P(\mu_{Test} < 0) \ge 0.975$.

Primary hypothesis 4:

The null and alternative hypothesis for binocular near HLHC visual performance to test for superiority of the Test lens relative to the pre-defined threshold of 0.17 logMAR is as follows:

$$H_o$$
: $\mu_{Test} \ge 0.17 \log MAR$
 H_A : $\mu_{Test} < 0.17 \log MAR$

Superiority will be declared if the upper limit of the 95% confidence interval of the adjusted mean for the Test lens is below 0.17 logMAR. i.e. $P(\mu_{Test} < 0.17) \ge 0.975$.

Primary hypothesis 5:

The null and alternative hypothesis for binocular distance HLHC visual performance to test for superiority of the Test lens relative to the pre-defined threshold of 0.17 logMAR is as follows:

$$H_o$$
: $\mu_{Test} \ge 0.17 \log MAR$
 H_A : $\mu_{Test} < 0.17 \log MAR$

Superiority will be declared if the upper limit of the 95% confidence interval of the adjusted mean for the Test lens is below 0.17 logMAR. i.e. $P(\mu_{Test} < 0.17) \ge 0.975$.

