14.6. Secondary Analysis

CLUE Vision, Comfort and Handling Scores

Vision, Comfort and Handling scores after approximately 2-weeks in the optimized lenses will be analyzed separately using a linear mixed model. event (visit 1: baseline, visit 2: 1-wk non-optimized, visit 3: 1-wk optimized and visit 4: 2-wk optimized), strata (hyperope and myope) and the interaction between event and strata will be included in the model as fixed effects. Other covariates such as age, gender and add power may be included when appropriate. Site will be included as a random effect (G-side). Residual errors between measurements within the same subject across event will be model using one of the following:

- Unstructured (UN)
- Compound Symmetric (CS)
- Heterogenous Compound Symmetric (CSH)
- Spatial Power (SP(POW))

The structure that returns the lowest corrected Akaike's Information Criterion (Keselman et al. 1998)¹³ will be selected as the structure that best fits the data. The Kenward and Roger method will be used for the calculation of the denominator of degrees of freedom.¹⁴

Hypothesis Testing

The null and alternative hypotheses for non-inferiority are as follows and will be conducted separately for each strata (hyperopes and myopes) and CLUE vision, comfort and handling:

$$H_0$$
: $\Delta \le -5$
 H_0 : $\Delta > -5$

Where Δ is the change from baseline to 2-week follow-up (2-week follow up minus baseline). Non-inferiority of the 2-week follow-up CLUE score relative to the baseline CLUE scores of subjects' habitual lens was concluded if the lower limit of the 95% CI was above -5 (Pr: 2 – wk minus baseline > -5,) > 0.975.

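### H1 and H2 are decided on a baseline-adjusted mean in a single-arm study; with the plan's own inputs, false success on H1 is about 1.8 to 2.8 times nominal, depending on choices the plan leaves open

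*Combined protocol and SAP*

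**What the plan says.** Section 5.1 says "This is a single-arm study". The first primary hypothesis in section 2.3 is that "the mean overall quality of vision score with the Test lens will be statistically better than 40 points on CLUE scale for myopic subjects"; the second is the same statement for hyperopes with a threshold of 32. Section 14.2 sizes both with a one-sample t-test.

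Section 14.5 analyses CLUE vision with one linear mixed model for both strata. Its fixed effects begin "Baseline vision scores, event (visit 1: baseline, visit 2: 1-wk non-optimized, visit 3: 1-wk optimized and visit 4: 2-wk optimized), strata (hyperope and myope") and add the event-by-strata interaction. Age, gender and add power are optional covariates, and site is a random effect. H1 is met if "the lower limit of the 95% confidence interval of the adjusted mean for the Test lens is greater than 40", and H2 if "the lower limit of the 95% confidence interval of the adjusted mean for the Test lens is greater than 32". The section does not say at which baseline score the adjusted mean is evaluated, or whether its standard error allows for the sampling of baseline.

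The CLUE vision model in section 14.6 has event, strata and their interaction but no baseline covariate. For acuity, section 14.5 makes position the only fixed effect and then adds: "Other baseline characteristics known of importance such as age, gender and add power may be included as covariates when appropriate".

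**The concern.** In a randomised comparison, adjusting for baseline sharpens the difference between arms. Here each stratum has one mean and the comparator is a constant, so there is no contrast to sharpen. Two things follow.

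- **Standard error.** The model conditions on the baseline scores that happened to be sampled. It removes the variance explained by baseline from the interval, although that variance is still part of the sampling error of the stratum mean named in 2.3. Kenward-Roger degrees of freedom do not put it back, because they also condition on the covariates.
- **Location.** Software usually evaluates adjusted means at the overall covariate mean. If the strata differ at baseline, each stratum is assessed at a baseline that is not its own, against a threshold specific to that stratum. The H1 result would then depend partly on the hyperopes' baseline scores.

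At stake is whether the primary rule tests the quantity named in 2.3 at the stated error rate.

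**Working it through.** **Inputs.** Table 7, CLUE vision, baseline then 2-week: myopes 42.9 (15.43) and 55.1 (20.73); hyperopes 45.5 (14.71) and 47.3 (18.65). Completers: 45 and 35 (14.2). Baseline-to-follow-up correlation ρ: 0.3 and 0.5, the Table 9 scenarios. Assumed: follow-up scores only as the response, no site effect, complete data, true means exactly 40 and 32.

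**1. The plan's own figure.** Table 8 gives n = 22 and 80.9% power for H1. A one-sample t-test with difference 55.1 − 40 = 15.1 and SD 20.73 gives 80.7% at n = 22 with one-sided α of 0.01. (Two-sided 0.01, as worded, would need 26; that is a separate point.) So the sample size used the raw SD, with no baseline adjustment.

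**2. Standard error for myopes.**
- Plain mean: 20.73/√45 = 3.09.
- Pooled within-stratum sums: Sxx = 44·15.43² + 34·14.71² ≈ 17,833; Sxy = ρ(44·15.43·20.73 + 34·14.71·18.65) ≈ 23,402ρ; Syy = 44·20.73² + 34·18.65² ≈ 30,734.
- Residual variance = (Syy − Sxy²/Sxx)/77. At ρ = 0.3: (30,734 − 2,764)/77 = 363.2, so SE = √(363.2/45) = 2.84. At ρ = 0.5: (30,734 − 7,677)/77 = 299.4, so SE = 2.58.
- Part of the narrowing comes from pooling variance with the less variable hyperopes: without baseline, √(30,734/78)/√45 = 2.96. The rest is the baseline covariate.
- In simulation the model SE averages 2.83 and 2.57, while the adjusted mean actually varies with SD 3.04 and 2.91.

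**3. Shift at the pooled baseline.** Pooled baseline = (45·42.9 + 35·45.5)/80 = 44.04. This is 1.14 above the myopes' own mean and 1.46 below the hyperopes'. The common slope Sxy/Sxx = 1.312ρ is 0.39 or 0.66. The shift is +0.45 or +0.75 for myopes and −0.58 or −0.96 for hyperopes.

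**4. False success on H1, 95% CI (nominal 2.5%).** Approximately P{Z > (1.99·SE − shift)/true SD}.
- ρ = 0.3: (1.99·2.83 − 0.45)/3.04 = 1.70, giving 4.4%.
- ρ = 0.5: (1.99·2.57 − 0.75)/2.91 = 1.50, giving 6.7%.

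Simulated single-visit ANCOVA:

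| Case | ρ = 0.3 | ρ = 0.5 |
|---|---|---|
| H1, pooled baseline, Table 7 gap | 4.6% | 6.8% |
| H1, evaluated at the myopes' own baseline | 3.7% | 5.0% |
| H1, stratum baselines equal | 3.3% | 4.2% |
| H1, Table 7 gap reversed | 2.6% | 2.3% |

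Repeated-measures versions with visits 2 to 4 as the response reach about 7% at ρ = 0.5. H2 at the pooled baseline is 1.1% to 1.5%. The unadjusted myope mean gives 2.4% to 2.7%.

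**5. At a 99% CI**, the Bonferroni level in 14.2, H1 is about 1.1% and 2.2% against 0.5% nominal. Changing the confidence level alone does not cure the fault.

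**The case against.** **The upward shift is conditional.** The evaluation point is not stated, and the 2.6-point gap in Table 7 compares two different historical studies. At these sample sizes its SE is √(15.43²/45 + 14.71²/35) = 3.4, so a gap of the opposite sign has about a 22% chance. H1 would then be near nominal and H2 inflated instead (about 3% to 5%). This stands: the direction is not fixed.

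**Site is left out.** A refit with a random site effect (assumed 5 or 8 sites, site SD 0 or 4; the documents give neither) gave H1 at 3.3% to 4.1% for ρ = 0.3 and 5.2% to 5.9% for ρ = 0.5, with Monte Carlo error of about 0.5 points. The inflation is reduced but still present.

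**The practical effect is small.** The planned mean is (55.1 − 40)/3.09 = 4.9 SEs above the threshold, and all five hypotheses must be met. This limits the severity; it does not make the rule valid.

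A reader might infer more than the documents support:
- *A fivefold error rate.* At the 95% CI, with follow-up scores as the response, this needs a correlation of about 0.7; Table 9 uses 0.3 and 0.5. The event list also names the baseline visit. If that row is kept as a response while baseline is a covariate, H1 is 5.1% to 8.0% under unstructured or heterogeneous compound symmetry and 7.5% to 11.2% under compound symmetry. That is a separate defect and is not counted here.
- *Inflation on H2.* In the follow-up-only model the hyperope SE is 3.21 against a true SD of 3.10 (ρ = 0.3) and 2.91 against 2.93 (ρ = 0.5), so it is not materially understated, and at the Table 7 gap the mean moves down.
- *The same error on H3 to H5.* Covariates there are optional, and the documents give no correlation with acuity from which to compute a rate.

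**Conclusion.** The concern holds for H1, in conditional form, and should be fixed. The primary rule tests a different quantity from the stratum mean that was hypothesised and powered, with an interval too narrow for that mean. Under the assumptions listed with the inputs, evaluation at the pooled baseline and a Table 7 gap, the error rate is about 1.8 to 2.8 times nominal. With equal stratum baselines it is about 1.3 to 1.7 times (3.3/2.5 to 4.2/2.5). H2 is affected in the opposite direction: it is conservative, and tested on a mean displaced downward. Size and direction depend on the evaluation point, the actual baseline gap, the correlation and the site effect, none of which the plan fixes. The rates are for H1 alone at a true mean of exactly 40; they are not the false-success rate of the whole study.

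**What to change.** In 14.5, decide H1 and H2 on the Visit 4 stratum means without the baseline score or any other covariate. Either of two forms would do:
- a one-sample t interval within each stratum, which matches 14.2; or
- the stratum means at Visit 4 from a model of the 14.6 type, with unstructured covariance estimated separately by stratum.

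The second form keeps site and the earlier visits of subjects who drop out. It must not fall back on compound symmetry or spatial power pooled over visits and strata, both of which 14.6 allows. If the SDs at visits 2 and 3 equal those at Visit 4, pooled compound symmetry gives SD √{[44(15.43² + 3·20.73²) + 34(14.71² + 3·18.65²)]/(4·78)} = 18.8 in place of 20.73, and H1 would again run at about 3.8%.

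Keep covariate-adjusted fits, including any for H3 to H5, as supportive only.

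The cost is a change of wording and a somewhat wider interval (SE about 3.09 in place of 2.84 or 2.58). Table 8 is unchanged because it already uses the raw SDs. With Table 7 means, power at 45 and 35 completers is 98.3% for H1 and 97.9% for H2 at two-sided 0.01, and above 99% for both at 0.05.

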4.3. Enrollment Target and Study Duration

Approximately 50 myopic subjects with against-the-rule astigmatism will be enrolled, with the aim that at least 45 will complete the study. Approximately 40 hyperopic subjects with against-the-rule astigmatism will be enrolled, with the aim that at least 35 will complete the study. Subjects to be enrolled will have -1.00 D to -1.50 D of astigmatism in both eyes with $90^{\circ}\pm30^{\circ}$ axis

Lenses in minus powers and plus powers will be evaluated in two separate phases of the study which may run at different times depending on when lenses become available. Each phase of the study will last approximately 3 months. Each individual subject is expected to be in the study for approximately 3 weeks. Lens will be worn as daily disposable and will be replaced daily.

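### The acuity model for hypotheses 3 to 5 leaves out the myope/hyperope stratum: a modest precision cost, and no final stratum-level acuity estimate

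*Combined protocol and SAP*

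**What the plan says.** Section 14.5 uses one linear mixed model for binocular acuity at three distances, in which position "will be included as the only fixed effect". Site is random. The plan adds: "Other baseline characteristics known of importance such as age, gender and add power may be included as covariates when appropriate". Refractive stratum is not named there.

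In the same section the CLUE vision model is different: "strata (hyperope and myope) and the interaction between event and strata will be included in the model as fixed effects". Section 14.6 treats the secondary CLUE scores the same way.

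The acuity hypotheses in section 2.3 are pooled. For distance, "logMAR visual acuity of the test lens will be statistically better than 0.00 logMAR"; intermediate and near have the same form with 0.17. The decision rule for H3 in section 14.5 is that the "upper limit of the 95% confidence interval of the adjusted mean for the Test lens is below 0 logMAR". Section 2.3 also states: "All primary hypotheses must be met in order to satisfy the study objective". These include H2, which concerns CLUE vision in hyperopes only.

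Sections 4.1 and 14.2 set targets of 45 myopic and 35 hyperopic completers. Section 4.3 adds: "Lenses in minus powers and plus powers will be evaluated in two separate phases of the study". Section 14.8 plans a descriptive read of all primary and secondary endpoints once the hyperopes have finished.

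**The concern.** Stratum is a design factor here. Its shares are set by quota, it determines which lenses are worn, and it may coincide with calendar phase. Acuity is the only primary or secondary endpoint whose model ignores it, and no reason is given.

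Two things follow. First, with the 45:35 mix fixed in advance, the between-stratum difference is not sampling error of the pooled mean, yet a position-only model counts it as residual variance. Second, the final analysis specifies no adjusted acuity mean or interval for either stratum. A reader of the report could take a pooled pass as evidence for the plus-power lenses when it need not be.

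**Working it through.** **Inputs.** Table 6 gives distance mean -0.048, SD 0.0943; intermediate -0.015, SD 0.1183; near 0.097, SD 0.1318. The margins from the thresholds 0.00, 0.17 and 0.17 are therefore 0.048, 0.185 and 0.073. Myopes make up p = 45/80 = 0.5625, so p(1-p) = 0.2461. The documents give no myope/hyperope acuity difference d, so d is assumed over a range. They also do not settle whether the Table 6 SD is total or within-stratum, so both readings are used for pass rates. Site effects are ignored.

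**The plan's own figures.** An exact one-sample t calculation with these inputs reproduces Table 8 (distance 42, 80.6%; intermediate 7, 80.1%; near 36, 80.7%) at one-sided 0.01. At the two-sided 0.01 stated in section 14.2, the same sizes give 72.2%, 66.2% and 72.2%. Section 14.5 decides on a 95% interval, without the Bonferroni level. That is a separate matter, but it is why results are given at both levels below.

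**Precision.** Take 0.0943 as the total SD. The between-stratum share of variance is p(1-p)d²/SD², and the standard error is inflated by 1/√(1 - share). The unadjusted standard error is 0.0943/√80 = 0.01054.

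| Assumed d (logMAR) | Share of variance | SE with strata | Inflation without strata |
|---|---|---|---|
| 0 | 0% | 0.01054 | 0% |
| 0.020 | 1.1% | 0.01048 | 0.6% |
| 0.048 | 6.4% | 0.01020 | 3.4% |
| 0.085 | 20.1% | 0.00942 | 11.9% |

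For d = 0.048: 0.2461 × 0.048² / 0.0943² = 0.0638, and 1/√0.9362 = 1.034.

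With 80 completers and the Table 6 values, unadjusted power is 99.4% for distance and 99.8% for near under the 95% interval (97.0% and 98.9% at two-sided 0.01).

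**What a pooled pass shows.** Put hyperopes exactly at 0.00 and use 0.0943 as the within-stratum SD.

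- *Myopes at -0.048.* The pooled mean is 0.5625 × -0.048 = -0.027. The unadjusted SD is √(0.0943² + 0.2461 × 0.048²) = 0.0973, so its standard error averages 0.0109. A pass needs a pooled mean below about -1.990 × 0.0109 = -0.0216. The pooled mean really varies with standard error 0.01054, so z = (0.027 - 0.0216)/0.01054 ≈ 0.51, a probability of about 0.69.
- *Myopes at -0.085.* The pooled mean is -0.048. The same steps give SD 0.1034, standard error 0.0116, cut-off -0.0230 and z ≈ 2.37, a probability of about 0.99.

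Simulation with 45 and 35 subjects agrees:

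| Myope mean | H3 pass, 95% interval | H3 pass, two-sided 0.01 | 95% interval, strata added, observed-margin weights |
|---|---|---|---|
| -0.048 | 69% | 44% | 71% |
| -0.085 | 99.0% | 94.5% | 99.4% |

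Reading 0.0943 as the total SD raises the first row to 72%, 47% and 74%, and the second to 99.8%, 98.0% and 99.9%.

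With hyperopes at 0.17 and myopes at the Table 6 mean, near passes in 76-79% and intermediate in about 100% under the 95% interval.

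In these distance and near scenarios, among trials where the pooled test passes, the hyperope 95% interval fails to clear the threshold in 96-98%.

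**The case against.** The case against is substantial.

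- **Pooling is the stated target.** H3 to H5 concern the test lens overall, and each acuity threshold is common to both groups. CLUE needs strata because its thresholds differ (40 and 32). This stands: a pooled pass with hyperopes at the threshold is not a type I error for H3 as written.
- **A strata term does not cure it.** This also stands. With observed-margin weights the pass rate rises slightly (69% to 71%; 99.0% to 99.4%), because the interval narrows around the same mean.
- **Study success needs more.** A reader might infer that the trial could succeed with probability 70% or 99% while the plus-power lenses sit at the threshold. The documents do not support that. Those are pass rates for one hypothesis, and all five must be met, including the hyperope CLUE hypothesis. That hypothesis, however, guards subjective vision and not acuity.
- **The precision loss changes little.** It rests on an undocumented difference, is zero without one and errs on the conservative side. Section 14.2 required only 42 completers. This stands.
- **Hyperope acuity is not unseen.** Section 14.8 gives a descriptive hyperope read, and the covariate sentence in 14.5 is open-ended enough to admit stratum. Both are true, but neither pre-specifies an adjusted mean or interval by stratum for the final analysis.

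**Conclusion.** The point holds as a low-cost improvement worth considering. The position-only model omits a quota-fixed design factor that the CLUE models include. The cost in precision is 0% to about 12% of the distance standard error over assumed differences of 0 to 0.085 logMAR. It does not threaten power at 80 completers.

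The more useful part concerns interpretation. Because H3 to H5 are pooled, passing them says little about a single lens range: about 70% to 99% of trials pass H3 with hyperopes exactly at 0.00 (44% to 95% at two-sided 0.01). The range depends on assumed myope means of -0.048 and -0.085, a within-stratum SD of 0.0943 and no site effects. The cause is the pooled wording and not the missing term. It would be wrong to conclude that the planned test is invalid or that a strata term would prevent such a pass.

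**What to change.** In section 14.5, make the acuity fixed effects position, strata and position by strata. Test H3 to H5 on the pooled least-squares mean at each position with observed-margin weights, which leaves the hypotheses unchanged. Report each stratum's adjusted mean and 95% interval at each position as supportive results, and limit any acuity conclusion about the plus-power or minus-power lenses to what those intervals show. Settle the wording before the hyperope interim read, so that the choice cannot look data-driven.

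The cost is a wording change and three fixed-effect degrees of freedom (one for strata, two for the interaction), with no new data or subjects. The stratum intervals are less certain to clear the thresholds than the pooled one. If each stratum truly has the Table 6 mean and SD, 35 hyperopes clear distance in 83% and near in 89% of trials, and 45 myopes in 92% and 95%. That is a reason to keep them supportive.

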14.2. Sample Size Justification

This study was designed and powered to demonstrate that the binocular high luminance high contrast, visual performance (logMAR) of the Test lens at distance (4 meters), intermediate (64 cm) and near (40 cm) after 2-week of lens wear in the optimized lenses is superior to 0.00, +0.17 and +0.17 logMAR, respectively. Additionally, this study was also powered to show that CLUE vision scores for the Test lens for the hyperopic population is greater than 32 points and greater than 40 points for the myopic population. The sample size calculation included

two historical studies, and Previous hyperopic data was not available for the Test lens, therefore, data from was used because it evaluated lenses with a similar lens design on a hyperopic population. Data from was used for the myopic population since this study evaluated lenses with the same lens design and similar material as the current Test lens on a population of myopic subjects.

Table 6: Historical Binocular High Luminance High Contrast Visual Performance – 2-Week Follow-up

Chart Position	Mean	SD*	Minimum	Maximum
Distance (4 M)	-0.048	0.0943	-0.220	0.280
Intermediate (64 cm)	-0.015	0.1183	-0.240	0.320
Near (40 cm)	0.097	0.1318	-0.200	0.500

^{*}SD: Standard Deviation

Table 7: Historical CLUE Scores – 2-Week Follow-up

CLUE Domain	Strata	Baseline	2-Week Follow-up
		Mean (SD*)	Mean (SD*)
Vision	Hyperope	45.5(14.71)	47.3(18.65)
	Myope	42.9(15.43)	55.1(20.73)
Comfort	Hyperope	50.7(19.70)	60.9(22.38)
	Myope	54.5(20.39)	62.7(21.95)
Handling	Hyperope	50.9(17.26)	56.6(21.12)
	Myope	56.9(16.49)	70.6(18.02)

^{*}SD: Standard Deviation

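### The acuity model lets AICC choose a common-variance structure although the planning SDs differ by 40% between near and distance; the effect is small, and prespecifying UN removes it at no real cost

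*Combined protocol and SAP*

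**What the plan says.** Section 14.5 (LogMAR Visual Acuity) analyses distance, intermediate and near acuity in one linear mixed model. On the mean structure it says "Position(distance/intermediate/near) will be included as the only fixed effect", with site as a random effect and optional baseline covariates. As residual structures that may be considered it lists "Homogenous compound symmetry (CS) and Unstructured covariance structure (UN", and then says "The structure that returns the lowest Akaike Information Criteria Corrected (AICC) will be selected as the structure that best fit the data". Each of the three acuity hypotheses is decided by whether the upper limit of the 95% interval for one position's adjusted mean lies below its threshold. Section 2.3 requires every primary hypothesis to be met.

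For the CLUE vision model the same section also lists "Heterogenous Compound Symmetric (CSH" as a candidate. The acuity paragraph does not name it.

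Table 6 in Section 14.2 ("Historical Binocular High Luminance High Contrast Visual Performance") gives historical SDs of 0.0943 (distance), 0.1183 (intermediate) and 0.1318 (near). The acuity sample sizes in Table 8 rest on these.

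**The concern.** Each position carries its own primary hypothesis and its own interval, so each interval needs that position's variance. Homogeneous CS cannot supply it: it replaces three variances with their average. If the trial's SDs resemble Table 6, a CS fit makes the near test too lenient and the distance test too strict. Distance is also the acuity endpoint with the largest required sample in Table 8 (42). The Kenward-Roger method works within the chosen structure and does not restore position-specific variances. What is at stake is the standard error of two of the three acuity tests in those trials where AICC prefers CS.

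**Working it through.** **Inputs.** Means, SDs and thresholds from Section 14.2 and Table 6; 80 target completers from Section 14.2; the 95% interval rule from Section 14.5. The between-position correlation is not given and is varied from 0 to 0.8 as an assumption.

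**1. The plan's own figures.** Table 8 lists 42, 7 and 36 subjects for distance, intermediate and near, with power 80.6%, 80.1% and 80.7%. A one-sample t-test with each position's own SD has noncentrality (difference / SD) × √n:
- distance: (0.048 / 0.0943) × √42 = 3.30
- intermediate: (0.185 / 0.1183) × √7 = 4.14
- near: (0.073 / 0.1318) × √36 = 3.32

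At one-sided 0.01 these give 80.6%, 80.1% and 80.7%, an exact match. Two-sided 0.01, as worded, would need 49, 9 and 42; that is a separate matter. The relevant fact here is that the study was sized with separate SDs.

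**2. What CS does to the intervals.** With complete data the CS variance is the mean of the three variances:

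(0.0943² + 0.1183² + 0.1318²) / 3 = 0.01342, so the common SD is 0.1158.

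Interval width under CS relative to the Table 6 SD:
- distance: 0.1158 / 0.0943 = 1.23 (23% too wide)
- intermediate: 0.1158 / 0.1183 = 0.98
- near: 0.1158 / 0.1318 = 0.88 (12% too narrow)

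At N = 80 the half-width under CS is 1.96 × 0.1158 / √80 = 0.0254 everywhere, against 0.0207 at distance and 0.0289 at near with separate SDs. If CS were always fitted, one-sided error would be 1 − Φ(1.96 × 0.879) = 4.2% at near and 1 − Φ(1.96 × 1.228) = 0.8% at distance, against 2.5%.

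**3. How often AICC picks CS.** With n = 3 × 80 − 3 = 237 and penalty 2kn / (n − k − 1), the penalties are 4 × 237 / 234 = 4.05 for CS (k = 2) and 12 × 237 / 230 = 12.37 for UN (k = 6). CS is therefore chosen when UN improves −2 REML log-likelihood by less than 8.31. This was simulated with 40,000 trials per correlation, N = 80, complete normal data with the Table 6 SDs, no site effect, no covariates, t-tests on N − 1 df for UN and Satterthwaite df for CS.

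| Correlation | AICC picks CS | Near error, all trials | Distance error, all trials | Near error in CS-selected trials: CS / UN |
|---|---|---|---|---|
| 0 | 25% | 2.9% | 2.1% | 4.4% / 3.1% |
| 0.3 | 21% | 2.8% | 2.3% | 4.7% / 3.4% |
| 0.5 | 13% | 2.6% | 2.3% | 4.5% / 3.4% |
| 0.7 | 4% | 2.6% | 2.4% | 5.1% / 4.0% |
| 0.8 | 0.7% | 2.6% | 2.4% | too few trials |

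Errors are one-sided. UN used in every trial gives about 2.5% at each position. The conditional figures at 0.7 rest on about 1,400 trials and are imprecise.

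**4. Effect on the conclusion.** At the Table 6 means, power to pass all three acuity tests is about 99% with UN and with AICC selection. The two approaches reach a different joint acuity conclusion in under 0.2% of trials at every correlation.

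**The case against.** The strongest reply is that this hardly affects the trial. UN is already a candidate, AICC between named structures is a cited method, and at N = 80 it selects UN in about 75% or more of trials. The property that matters is the error of the whole procedure, which moves by about 0.3 percentage points at most. Because every primary hypothesis must be met, a slightly lenient near test cannot by itself produce study success. All of this stands and sets the size of the point.

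Three stronger readings are tempting and are not supported:

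- A reader might infer that near error roughly doubles, from 2.5% to 4.4-5.1%, because of CS. Those figures describe only the trials in which CS is chosen, and these are the trials whose sample SDs happen to look alike. In the same trials UN itself gives 3.1-4.0%, so only part of the excess comes from CS.
- A reader might infer that the plan rules out CSH for acuity. Its list says what the structures may include, so CSH is unnamed but not excluded.
- A reader might infer that UN always reproduces the one-sample t-test used for sizing. It does so only with complete data, no covariates and no site variance, whereas the planned model has a random site effect and allows covariates.

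What the reply does not answer is why homogeneous CS should be a candidate at all, when the planning data point against it and separate variances cost so little.

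**Conclusion.** The point holds as a minor, free improvement. The stated rule can give primary acuity intervals a variance that does not belong to their position: about 23% too wide at distance and 12% too narrow at near relative to Table 6. How often depends on a correlation that the documents do not give: about one trial in four at 0, one in eight at 0.5, and under 1% at 0.8. Averaged over all trials, near error is about 2.6-2.9% and distance about 2.1-2.4%, and the joint acuity conclusion is almost never altered.

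The result assumes 80 completers, complete normal data, no site effect, and trial SDs like those in Table 6. Those are historical marginal SDs; residual SDs after site and covariates may differ. The error rates refer to the 95% interval rule as written in Section 14.5.

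**What to change.** In the LogMAR Visual Acuity paragraph of Section 14.5, prespecify UN as the residual covariance across the three positions, with CSH as the fallback if UN does not converge. Delete homogeneous CS and the AICC selection for this model, along with the open-ended list of structures. The CLUE models need no change on this account.

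The cost is one sentence in the plan and four more covariance parameters (6 instead of 2) on about 80 × 3 = 240 observations. In return each primary acuity interval uses its own position's variance, and a data-dependent choice is removed from three confirmatory tests.
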